9.2. Analysis Sets

The following analysis populations will be used for presentation and analysis of data.

- Safety Analysis Set is defined as all enrolled participants who have received at least 1 dose of study intervention (NIMP or IMP).
- Full Analysis Set is defined as all enrolled participants who were exposed to lerociclib during the study.
- Response Evaluable Analysis Set is defined as all enrolled participants who were exposed to lerociclib during the study and who had measurable disease at baseline.

All safety analyses will be assessed using the Safety Analysis Set. Tumor response endpoints will be assessed using the Response Evaluable Analysis Set. Progression-free survival, OS, and QoL will be assessed using the FAS.

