4.5 Analysis Sets

The following analysis populations will be used for presentation and analysis of data:

- Safety Analysis Set is defined as all enrolled participants who have received at least 1 dose of study intervention (IMP or NIMP).
- Full Analysis Set (FAS) is defined as all enrolled participants who were exposed to lerociclib (IMP) during the study.
- Response Evaluable (RE) Analysis Set is defined as all enrolled participants who were exposed to lerociclib during the study and who had measurable disease at baseline.

All safety analyses will be assessed using the Safety Analysis Set. PFS, OS and QoL will be assessed using the FAS. Tumor response endpoints will be assessed using the RE Analysis Set. As all participants are to receive the same treatment, all analyses will be summarized based on the planned treatment dose. Any deviations from planned treatment will be documented.

The FAS and Safety Analysis Set will be derived programmatically using study drug exposure data. The RE Analysis Set will be derived programmatically as determined by investigator assessment of baseline disease status using RECIST v1.1..

A summary of the number and percentage of participants by line of therapy for each analysis set will be presented.

A by-participant listing of analysis set details will be provided, including site, participant identifier, inclusion/exclusion flag for each set, and reason for exclusion from each set..

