4.10.2 RECIST Overall Response

The primary evaluation of efficacy endpoints will be based on the final assessment of timepoint Overall Response.

Extent of disease and tumor response will be assessed using Overall Response at each timepoint RECIST v1.1 ([Eisenhauer 2009](#)) as assessed by the Investigator (refer to Section 8.1.1 of the protocol). An Overall Response at each timepoint will be derived algorithmically based on the data entered for Target Lesions, Non-Target Lesions, and New Lesions. However, the Investigator can override this determination based on their clinical judgment of the participant at time of evaluation. In such cases the result of the RECIST algorithm will take precedence in the primary evaluation. The effect of any Investigator overrides will be explored as a sensitivity analysis.

. For participants with measurable disease at baseline the following timepoint responses are possible:

- Progressive Disease (PD)
- Stable Disease (SD)
- Partial Response (PR)
- Complete Response (CR)
- Not Evaluable (NE)

For participants who do not have measurable disease at baseline the following timepoint responses are possible:

- Progressive Disease (PD)
- Non-Complete Response / Non-Progressive Disease (Non-CR/Non-PD)
- Complete Response (CR)
- Not Evaluable (NE)

Once a RECIST v1.1 timepoint response of PD is observed all subsequent RECIST evaluations will not be used in analysis unless otherwise specified [REDACTED]

The primary evaluations of tumor response (ORR, CBR, DOR, and TTR) will be based on the RE set, which is limited to participants with measurable disease at baseline. [REDACTED]

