4.10.3 Efficacy Analyses

4.10.3.1 Objective Response Rate (ORR) and Clinical Benefit Rate (CBR)

The ORR defined as the percentage of participants achieving a confirmed CR or confirmed PR based on RECIST, Version 1.1.

Unless otherwise specified all analyses of ORR will be based on the best overall confirmed response. “Best response” is defined according to the following hierarchy:

- 1) CR
- 2) PR
- 3) SD/ Non-CR/Non-PD
- 4) PD
- 5) NE

The CBR is defined as the percentage of participants having achieved a confirmed CR, confirmed PR, or SD (for at least 24 weeks \pm 7 days).

The confirmed Best Overall Response, ORR, and CBR will be summarized by line of therapy along with the associated 2-sided exact 95% CIs based on the Clopper-Pearson method.

A forest plot of confirmed ORR by subgroup will be presented. Additionally, a swim lane plot as well as a table/waterfall plot showing the maximum percent change in target lesion reduction for each subject will be presented.

A by-participant listing of the best overall response data with ORR and CBR will be provided.

In addition, separate listings will also be provided for Target Lesions, Non-Target Lesions, and New Lesions for which these response assessments are conducted.

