4.12 Determination of Sample Size

Approximately 100 participants will be enrolled and dosed in the study with approximately 50 participants in each line of therapy (1L or 2L). Assuming at least 80% of participants have measurable disease, approximately 40 of the planned 50 participants will have measurable disease per line of therapy. This sample size will allow an estimate of ORR with the half width of the 95% CI of no larger than approximately 16%.

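### The main clinical benefit rate is confined to participants with measurable disease, and the visible text gives no rule for counting durable Non-CR/Non-PD

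*SAP*

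**What the plan says.** Both documents tie tumour response to the Response Evaluable (RE) set, meaning participants exposed to lerociclib who had measurable disease at baseline. Protocol 9.2: "Tumor response endpoints will be assessed using the Response Evaluable Analysis Set". SAP 4.5: "Tumor response endpoints will be assessed using the RE Analysis Set". SAP 4.10.2 names CBR explicitly among the primary evaluations that are "based on the RE set, which is limited to participants with measurable disease at baseline". The text directly after that sentence is redacted. PFS, OS and quality of life use the FAS.

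The inclusion and exclusion criteria (Protocol 5.1, 5.2) do not ask for measurable disease. SAP 4.12, like Protocol 9.4, plans on this basis: "Assuming at least 80% of participants have measurable disease, approximately 40 of the planned 50 participants will have measurable disease per line of therapy".

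SAP 4.10.2 gives participants without measurable disease four possible timepoint responses: PD, Non-CR/Non-PD, CR and NE. The best-response hierarchy in SAP 4.10.3.1 has a single third rank, "SD/ Non-CR/Non-PD". The CBR definition in that section counts confirmed CR, confirmed PR, or SD of at least 24 weeks (± 7 days) and does not mention Non-CR/Non-PD. The section also plans a by-participant listing of best overall response with ORR and CBR, and names no analysis set for it.

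**The concern.** The efficacy objective (Protocol Table 3, SAP 3.2) concerns 1L and 2L participants by line, and the CBR endpoint is a proportion of participants with no measurable-disease qualifier. The main estimate describes a subset of them.

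For ORR, duration of response and time to response the restriction is reasonable, because a partial response needs target lesions. CBR is different: it also credits lasting absence of progression, which can be judged without target lesions. The assessments needed are already collected and already feed PFS in the FAS.

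The definition is also incomplete. By the SAP's own lists, Non-CR/Non-PD cannot arise in the RE set, so ranking it with SD matters only outside that set. There the CBR rule does not say whether a durable Non-CR/Non-PD is a benefit. Anyone deriving a CBR flag for all treated participants, for the listing or for a supportive table, would have to choose. At stake are the population that the reported CBR describes, some precision, and the reproducibility of any CBR derived beyond the RE set.

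**Working it through.** **Inputs.** From the documents: 50 participants per line and a measurable share of at least 80% (Protocol 9.4, SAP 4.12); exact Clopper-Pearson 95% intervals (Protocol 9.3.3.2, SAP 4.10.3.1); a CBR of 73.7% at 150 mg BID in the earlier second-line fulvestrant study (Protocol 4.3), used only as an illustrative level. Assumed: a CBR of 60% to 90% in participants without measurable disease, and a count of 28/40 in step 5.

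**1. Reproduce the plan's figures.** 50 × 0.80 = 40 per line. The largest exact half-width at n = 40 (at 20/40) is 16.2 points. The normal approximation gives 1.96 × √(0.25/40) = 15.5 points. Both agree with the plan's figure of about 16%.

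**2. Number outside the main CBR.** 50 − 40 = 10 per line, or 20 of 100 overall. If 85%, 90% or 95% had measurable disease, the number per line would be 7.5, 5 or 2.5. No criterion enforces the 80%, so it could also exceed 10.

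**3. Precision, RE set against FAS.**

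| CBR level | n = 40 | n = 50 | Difference |
|---|---|---|---|
| 50% (20/40, 25/50), the maximum | 16.2 | 14.5 | 1.7 |
| near 73.7% (29/40, 37/50) | 14.6 | 12.9 | 1.7 |

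Entries are exact 95% half-widths in percentage points.

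**4. Possible shift in the estimate.** All-participant CBR = 0.8 × 73.7% + 0.2 × q, where q is the CBR without measurable disease.
- q = 60%: 58.96 + 12.0 = 71.0%, a shift of −2.7 points.
- q = 90%: 58.96 + 18.0 = 77.0%, a shift of +3.3 points.

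**5. Why the counting rule matters as well as the set.** Take an assumed 28/40 = 70.0% in the RE set (exact interval 53.5% to 83.4%) and add 10 participants without measurable disease. If 0, 5, 7 or 10 of them are counted as having benefit, the FAS result is 28/50 = 56.0%, 33/50 = 66.0%, 35/50 = 70.0% or 38/50 = 76.0%. Suppose 7 of the 10 have durable Non-CR/Non-PD and none has CR. The SAP's literal definition then gives 56.0%, and a rule that credits them gives 70.0% (interval 55.4% to 82.1%). In this illustration the undefined category moves the FAS result by 14 points.

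**The case against.** The strongest reply is that the restriction is prespecified, agrees between protocol and SAP, and fits the endpoint as written: PR and SD cannot occur without measurable disease. The study is descriptive, with no hypothesis test, and CBR is secondary. The excluded participants still contribute to PFS in the FAS. Protocol 9.3.3.3 plans survival estimates at 6-month intervals, and SAP 4.10.1.5 plans PFS by metastasis site, so durable non-progression in all treated participants will be visible at about the SAP's 24-week horizon. All of this stands, and it keeps the point modest. It does not supply a CBR for the population named in the objective, nor a rule for Non-CR/Non-PD.

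A reader might also infer more than the documents support:

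- **That these participants get no CBR result at all.** The SAP restricts the primary evaluations, and the adjoining redacted text may contain a supportive analysis. The by-participant listing may cover them too.
- **That 20% is a ceiling or an expected value.** It is the boundary of a planning assumption.
- **That the excluded group is the bone-only group.** Protocol 8.1.1.1 lets lytic or mixed bone lesions with a measurable soft-tissue component count as measurable.
- **That the estimate is biased because the group has a different prognosis.** Neither document says so; the 60% to 90% range is only a sensitivity range.
- **That the documents contradict each other on the analysis set.** They do not.

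**Conclusion.** On the visible text, the main CBR covers a narrower population than its objective, and the CBR definition leaves durable Non-CR/Non-PD unaddressed while the hierarchy beside it equates that category with SD. This is a limit on scope and a gap in definition, not an arithmetic error. At the planning boundary about 10 of 50 participants per line are affected, and using all 50 would narrow the exact half-width by about 1.7 points. A shift of −2.7 to +3.3 points is conditional on the assumed 60% to 90% and on applying 73.7%, a second-line fulvestrant figure, to the measurable group. That shift is small beside a half-width of about 14.6 points. The case for change rests on matching the objective and closing the definition at low cost, not on a demonstrated distortion.

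**What to change.** **Settle the SD duration first.** The protocol (Synopsis, Table 3, 9.3.3.2) uses at least 8 weeks, SAP 4.10.3.1 uses at least 24 weeks (± 7 days), and SAP 3.2 gives none. SAP 4.13 nevertheless reports no change from the protocol's statistical methods. One value is needed before it can be applied to Non-CR/Non-PD.

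**Then amend** SAP 4.5, 4.10.2 and 4.10.3.1, with matching CBR wording in SAP 3.2 and in the Protocol Synopsis, Table 3, 9.2 and 9.3.3.2:

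- Report CBR by line in the FAS.
- For participants without measurable disease, count confirmed CR, or Non-CR/Non-PD lasting the reconciled SD minimum, as benefit.
- Count NE or no post-baseline scan as no benefit.
- Show the RE-set CBR alongside, and say which of the two is the main analysis, since SAP 4.2.2 calls for one per endpoint.
- Leave ORR, duration of response and time to response in the RE set.

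If the redacted text already provides a CBR in the FAS, what remains is the counting rule and the choice of main analysis.

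**Cost.** Wording in the sections above and one more table by line; no new data.

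**Downside.** Non-CR/Non-PD is a less exact category than SD. Protocol 8.1.1 has bone-only participants scanned every 12 weeks, whereas the Schedule of Activities gives 8-weekly bone scans in the first 12 months; these provisions must be reconciled. On a 12-week schedule, an 8-week minimum would be ascertained differently from participants followed by 8-weekly CT. For both reasons the RE-set table should be kept.

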4.10.2.1 Confirmation of Response

Unless otherwise specified analyses of response will be based on confirmed response. Confirmation of an initial response (CR or PR) requires observation of an equal or better response, following adequate follow up time defined as ≥ 28 days, without intervening PD.

4.10.3 Efficacy Analyses

4.10.3.1 Objective Response Rate (ORR) and Clinical Benefit Rate (CBR)

The ORR defined as the percentage of participants achieving a confirmed CR or confirmed PR based on RECIST, Version 1.1.

Unless otherwise specified all analyses of ORR will be based on the best overall confirmed response. “Best response” is defined according to the following hierarchy:

- 1) CR
- 2) PR
- 3) SD/ Non-CR/Non-PD
- 4) PD
- 5) NE

The CBR is defined as the percentage of participants having achieved a confirmed CR, confirmed PR, or SD (for at least 24 weeks \pm 7 days).

The confirmed Best Overall Response, ORR, and CBR will be summarized by line of therapy along with the associated 2-sided exact 95% CIs based on the Clopper-Pearson method.

A forest plot of confirmed ORR by subgroup will be presented. Additionally, a swim lane plot as well as a table/waterfall plot showing the maximum percent change in target lesion reduction for each subject will be presented.

A by-participant listing of the best overall response data with ORR and CBR will be provided.

In addition, separate listings will also be provided for Target Lesions, Non-Target Lesions, and New Lesions for which these response assessments are conducted.

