3. OBJECTIVES AND ENDPOINTS

Table 3: Study Objectives and Endpoints

| Objectives | Endpoints |
|---|--|
| Primary To characterize the safety and tolerability of lerociclib in combination with endocrine therapy in participants with 1L and 2L HR+/HER2- mBC | 
 Incidence of AEs and SAEs |
| Secondary To investigate the efficacy of lerociclib in combination with endocrine therapy in participants with 1L and 2L HR+/HER2- mBC by line of therapy | 
 Objective response rate, defined as the proportion of participants with a best overall response of CR or PR according to RECIST v1.1 as assessed by Investigator Clinical benefit rate, defined as the proportion of participants with a best overall response of CR, PR, or SD (for at least 8 weeks) according to RECIST v1.1 as assessed by Investigator Progression-free survival, defined as the time from first dose of lerociclib until the date of documented PD or death, according to RECIST v1.1 as assessed by Investigator Overall survival, defined as the time from the date of first dose of lerociclib to the date of death due to any cause Duration of response, defined as the time from the date of first documented response until the date of confirmed PD or death, according to RECIST v1.1 as assessed by Investigator Time to response, defined as the time from first dose of lerociclib until the first documented response (CR or PR) |
| To further characterize the safety and tolerability of lerociclib in combination with endocrine therapy in participants with 1L and 2L HR+/HER2- mBC | 
 Change from baseline in clinical laboratory parameters (hematology, clinical chemistry, coagulation, fasting lipid panel, and urinalysis) Change from baseline in vital signs and 12-lead ECG parameters |

Table 3: Study Objectives and Endpoints (Continued)

| Objectives | Endpoints |
|---|--|
| To assess change from baseline in global health status and QoL in participants with 1L and 2L HR+/HER2- mBC by line of therapy | 
 • Change from baseline in the Global Health Status/QoL Scale Score of the EORTC-QLQ-C30 • Change from baseline in the Global Health Status/QoL Scale Score of the EORTC-QLQ-BR23 • Change from baseline in the Global Health Status/QoL Scale Score of the EQ-5D-5L • Change from baseline in the Global Health Status/QoL Scale Score of the FACIT Item GP-5 |

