9.3.3.2. Assessment of Tumor Response and Clinical Benefit

The ORR is defined as the percentage of participants achieving a confirmed CR or confirmed PR based on RECIST v1.1.

The CBR is defined as the percentage of participants having achieved a confirmed CR, confirmed PR, or SD (for at least 8 weeks).

Objective response rate and CBR will be summarized along with the associated 2-sided exact 95% CIs based on the Clopper-Pearson method.

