3.2 Endpoints

The following endpoints will be used to evaluate the efficacy and safety of the study treatment based on the study objectives:

| Objectives | Endpoints |
|---|---|
| Primary | |
| To characterize the safety and tolerability of lerociclib in combination with endocrine therapy in participants with 1L and 2L HR+/HER2- mBC. | 
 Incidence of adverse events (AEs) and serious adverse events (SAEs) |
| Secondary | |

| Objectives | Endpoints |
|---|--|
| To investigate the efficacy of lerociclib in combination with endocrine therapy in participants with 1L and 2L HR+/HER2- mBC by line of therapy. | 
 Objective response rate (ORR), defined as the proportion of participants with a best overall response of complete response (CR) or partial response (PR) according to Response Evaluation Criteria in Solid Tumors version 1.1 (RECIST v1.1) as assessed by Investigator Clinical benefit rate (CBR), defined as the proportion of participants with a best overall response of CR, PR, or stable disease (SD) according to RECIST v1.1 as assessed by Investigator Progression-free survival (PFS), defined as the time from first dose of lerociclib until the date of documented progression of disease (PD) or death, according to RECIST v1.1 as assessed by Investigator Overall survival (OS), defined as the time from the date of first dose of lerociclib to the date of death due to any cause Duration of response (DOR), defined as the time from the date of first documented response until the date of confirmed PD or death, according to RECIST v1.1 as assessed by Investigator Time to response (TTR), defined as the time from first dose of lerociclib until the first documented response (CR or PR) |
| To further characterize the safety and tolerability of lerociclib in combination with endocrine therapy in participants with 1L and 2L HR+/HER2- mBC. | 
 Change from baseline in clinical laboratory parameters (hematology, clinical chemistry, coagulation, fasting lipid panel, and urinalysis) Change from baseline in vital signs and 12-lead electrocardiogram (ECG) parameters Clinically significant findings on physical examination |

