3.2.2 Efficacy Variables

- Tumor evaluation assessments – measured at Screening; every 8 weeks (± 7 days) during the first 12 months and every 12 weeks (± 7 days) thereafter until disease progression, death, withdrawal of consent, loss to follow-up, participant/legally acceptable representative decision; and at end of treatment (EOT) (If PR/CR is reported, confirmation of response is required; confirmatory assessment should be performed ≥ 4 weeks after response is first documented)
- Global Health Status/QoL Scale Scores (EORTC-QLQ-C30, EQ-5D-5L, and FACIT Item GP-5) – recorded at Screening; on Day 1 of each cycle (before any other study procedures) until disease progression, death, withdrawal of consent, loss to follow-up, participant/legally acceptable representative decision; and at EOT
- Global Health Status/QoL Scale Score EORTC-QLQ-BR23 – recorded at Screening; on Day 1 of every other cycle (before any other study procedures) until disease progression, death, withdrawal of consent, loss to follow-up, participant/legally acceptable representative decision; and at EOT

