4.10.1.3 Visit Windows

Analysis visit windows will be created based on the schedule of assessments in the protocol (Appendix 6.1) as shown below. Any visits outside the visit window will be considered “Unscheduled” and not summarized at a scheduled visit. If multiple records are mapped to the same visit, the one closest to the date of the scheduled assessment will be used. If there is an equal distance from the date of the scheduled assessment, the latest record will be used.

| Visit | Study Day Window |
|------------------|--|
| Screening | [-42, -1] |
| Cycle 1 Day 1 | 1 |
| Cycle 1 Day 15 | [13, 17] |
| Cycle 2 Day 1 | [27, 31] |
| ... | [expected day – 2 days, expected day + 2 days] |
| EOT/ED | [last dose day, last dose + 15 days] |
| Safety Follow-up | [last dose + 25 days, last dose + 35 days] |

For tumor evaluations, the following windows will be implemented:

| Visit | Study Day Window |
|---|--|
| Screening | [-42, -1] |
| Cycle 3 Day 1 | [50, 64] |
| Every 2 cycles (8 weeks) during first 12 months and every 3 cycles thereafter (12 weeks) until EOT/ED | [expected day – 7 days, expected day + 7 days] |
| EOT/ED | [last dose day, last dose + 15 days] |

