4.13 Changes in the Conduct of the Study or Planned Analysis

This SAP is based on the Study EQ132-201 protocol Version 3.0, Amendment 3, dated February 27, 2023. This amendment is considered substantial, based on the criteria set forth in Article 10(a) of Directive 2001/20/EC of the European Parliament and the Council of the European Union. However, it does not significantly impact analysis endpoints or methodology.

In addition, no changes to the statistical methods detailed in the study protocol have been implemented in this document.

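### Clinical benefit rate counts stable disease from 8 weeks in the protocol but from 24 weeks in the SAP analysis section, and SAP 4.13 says that no method changed

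*SAP*

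**What the plan says.** The protocol gives the same SD duration in three places. The synopsis and Table 3 (section 3) use "best overall response of CR, PR, or SD (for at least 8 weeks) according to RECIST v1.1 as assessed by Investigator". Section 9.3.3.2 reads "The CBR is defined as the percentage of participants having achieved a confirmed CR, confirmed PR, or SD (for at least 8 weeks".

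The SAP gives two other wordings. Its endpoint table (3.2) uses "best overall response of CR, PR, or stable disease (SD) according to RECIST v1.1 as assessed by Investigator", with no minimum duration. Its analysis section (4.10.3.1) uses "percentage of participants having achieved a confirmed CR, confirmed PR, or SD (for at least 24 weeks", followed by ± 7 days.

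SAP 4.13 states that "no changes to the statistical methods detailed in the study protocol have been implemented in this document", and the SAP revision history does not mention CBR. All of this is current text, and the SAP names protocol Version 3.0 as its basis.

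Tumor assessments are scheduled "every 8 weeks (± 7 days) during the first 12 months" (SAP 3.2.2). The first post-baseline row of the tumor window table in SAP 4.10.1.3 is "Cycle 3 Day 1 | [50, 64", that is, Study Days 50 to 64.

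**The concern.** No single CBR table can follow both protocol 9.3.3.2 and SAP 4.10.3.1. Under the protocol, one non-progressing scan at about week 8 is enough. Under the SAP, the participant must stay stable through about three scan intervals. Section 9 of the protocol leaves technical detail to the SAP, but tripling a threshold is a change of definition, and SAP 4.13 denies that any such change was made.

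The SAP wording also leaves two choices to the programmer. A tolerance of ± 7 days attached to a minimum does not give one cut-off. And nothing says whether SD lasts until the last scan without progressive disease (PD) or until the date of PD.

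What is at stake is the meaning of one secondary endpoint, reported by line of therapy with exact confidence intervals. The study is open-label, so the rule should be settled, and seen to be settled, before the data are summarized.

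**Working it through.** **Inputs.** SD durations of 8 and 24 weeks and the scan schedule are as quoted above. Median PFS is 24 months (protocol 1.1 and 4.1; SAP 3.1.2), the only PFS assumption in the documents and not split by line. About 40 participants per line have measurable disease (SAP 4.12), and CBR is analyzed in that set (SAP 4.10.2). Other medians and response rates below are assumptions. One month is taken as 52.1775/12 = 4.348 weeks.

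**1. The plan's own precision figure.** The worst case is 50% with n = 40. The Wald half-width is 1.96 × √(0.25/40) = 15.5 points. The largest Clopper-Pearson half-width is 16.2 points (20/40: 33.8% to 66.2%). The stated figure of approximately 16% is reproduced. The documents give no expected CBR.

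**2. Upper bound on the shift from 8 to 24 weeks.** With exponential PFS, S(t) = 2^(−t/median). Progression between weeks 8 and 24 can remove at most S(8) − S(24) from the CBR. This is an upper bound because a confirmed responder counts under either rule, even with early progression.

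**3. Allowing for responders.** Suppose responders have no event before week 24 and non-responders have the median shown. The shift is then (1 − ORR) × [S(8) − S(24)], taken here for an assumed ORR of 50% to 20%.

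| Median PFS | S(8 wk) | S(24 wk) | Upper bound | Of 40 participants | With ORR 50% to 20% |
|---|---|---|---|---|---|
| 24 months (documents) | 94.8% | 85.3% | 9.6 points | 3.8 | 4.8 to 7.6 points |
| 18 months (assumed) | 93.2% | 80.9% | 12.3 points | 4.9 | 6.2 to 9.8 points |
| 12 months (assumed) | 89.9% | 72.7% | 17.2 points | 6.9 | 8.6 to 13.8 points |
| 9 months (assumed) | 86.8% | 65.4% | 21.4 points | 8.6 | 10.7 to 17.1 points |

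Differences use unrounded values (9.56 at 24 months). An upper bound of 10 points needs a median of about 22.8 months or less; 20 points needs about 9.9 months or less.

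**4. SD of any duration against SD of at least 8 weeks.** The earliest scheduled first scan is Day 50, 7 weeks after Day 1. S(7) − S(8) is 0.6 points at a 24-month median and 2.2 points at an assumed 6 months. The SAP 3.2 wording therefore gives nearly the protocol's result.

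**5. The cut-off day.** Under the SAP's convention the first dose is Day 1, so week 8 is Day 1 + 56 = 57, the center of [50, 64]. Week 24 is Day 1 + 168 = 169, with window 162 to 176. A participant stable at an on-schedule scan on Day 165 passes with the 7-day allowance and fails a strict Day 169 rule.

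**6. How SD duration is counted.** A participant stable at week 16 with PD on the week-24 scan has 16 weeks of SD to the last non-PD scan, but 24 weeks to the PD date. The share progressing in that interval is S(16) − S(24): 89.9% − 85.3% = 4.7 points (unrounded) at 24 months, and 80.9% − 72.7% = 8.2 points at an assumed 12 months. These too are upper bounds, since they include confirmed responders.

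**The case against.** The best defense is that the operative analysis text names one rule, that the protocol sends technical detail to the SAP, and that planned by-participant response and lesion listings and a swim lane plot would let a reader apply either rule. This lowers the risk of concealed selection, and nothing in the documents suggests that the rule will be picked after seeing results. It does not settle which definition governs, and SAP 4.13 still denies a change that is visible in the text.

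Several stronger readings are tempting and are not supported:

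- **Three incompatible definitions.** There are three wordings, but the one without a duration is close to the 8-week rule because of the first scan window. The material conflict is 8 against 24 weeks.
- **A shift of 10 to 20 points.** The documents' own median gives an upper bound just under 10. Larger figures need shorter medians that the documents do not state, though a shorter median in one line is possible.
- **A shift as large as the sampling error.** The 16.2-point half-width applies near 50%. At higher rates it is smaller: 14.6 points at 29/40, 12.1 at 34/40 and 8.2 at 38/40. At the planning median, 9.6 points is also well short of 16.2.
- **A spoiled comparison with the earlier study.** Protocol 4.3 cites CBRs of 73.7% and 70.7% to compare two doses within that study. No comparison with this trial's CBR is planned, and that study's SD duration is not given.

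**Conclusion.** The contradiction is real and should be fixed. The protocol's 8-week rule and the SAP's 24-week rule cannot both be followed, SAP 4.13 is wrong on this point, and the 24-week rule lacks a cut-off day and a definition of SD duration.

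At the documents' 24-month median the choice lowers CBR through progression by at most about 9.6 points, or by about 5 to 8 points on the stated assumptions about responders. This rests on exponential PFS and one median for both lines. SD participants who leave assessment without PD between weeks 8 and 24 would also drop out of the numerator under the 24-week rule; the documents give no rate, so that part is not quantified.

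The effect is confined to one descriptive secondary endpoint. The primary safety endpoint, ORR, PFS and the sample size do not depend on it.

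**What to change.** Before database lock:

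1. State one SD duration in protocol 1.1, Table 3 and 9.3.3.2, and in SAP 3.2 and 4.10.3.1. Either duration resolves the conflict.
2. Define how SD duration is measured and give one cut-off day in place of the ± 7 days. If 24 weeks is kept, require the last non-PD assessment to fall on or after Study Day 162, the first day of the week-24 window. If 8 weeks is kept, the matching day is 57 − 7 = Day 50.
3. Report the other duration as a separately labelled supplementary rate.
4. If the 24-week rule is kept, list it in SAP 4.13 as a change from the protocol text on which the SAP was based.

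The cost is wording in both documents and one extra row in the response table. The downside of keeping 24 weeks is a headline CBR lower than under the 8-week rule.
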